Use liver biopsy as “golden standard” for pathological staging, to evaluate the clinical values of FibroTouch for the non-invasive and quantitative diagnosis of liver fibrosis and cirrhosis in CHB patients.

(II) Secondary Objective

- ◆ Difference between FibroTouch and FibroScan in the rate of d successful detection
- ◆ Difference between FibroTouch and FibroScan in the determined values
- ◆ Correlation between determined values of FibroTouch and ultrasonic semi-quantitative scores
- ◆ Performance of FibroTouch.

- Positioning accuracy evaluated by investigators
- Image displaying ability evaluated by investigators
- Scanning speed evaluated by investigators
- Detecting and calculating speed evaluated by investigators

III. Study Goal

To determine the diagnostic accuracy, specificity and sensitivity of FibroTouch for liver fibrosis assessment in CHB patients.

IV. Study Type

It's a prospective and multicenter study.

V. Anticipated Total Cases

According to publications on FibroScan and liver biopsy examination, the mean sensitivity and specificity are 0.61 and 0.90 respectively for different stages (four pathological stages: $\geq F4$, $\geq F3$, $\geq F2$ and F0-F1). Assuming a similar sensitivity and specificity of FibroScan and FibroTouch, the lowest clinically acceptable sensitivity and specificity is 0.55

and 0.8 respectively, when $\alpha=0.05$ and power=80%, 423 cases are required based on sensitivity; total 529 cases are required based on the determination effectiveness=80%; 328 cases are required based on specificity; total 410 cases are required based on the determination effectiveness=80%. By considering the center assignment, ≥ 600 qualified cases are included to guarantee 500 final statistical cases; and ≥ 100 cases are required for S0+S1, S2, S3, S4 and liver cirrhosis (compensatory stage) respectively. For each stage, the case is assigned as equally as possible.

VI. Study Time

One year (from May 2014 to May 2015).

VII. Case Assignment System (via central registration system)

Subject No. is assigned through IWRS system. After the investigator logs in the system and fills in the pathological stages, this system will, according to the completed contents, automatically assign the sole subject No. for this subject.

VIII. Statistical Analysis

Peking University Clinical Research Institute

IX. Study Design

(I) Inclusion Criteria

1. Age: 18—65 years, both gender.
2. History of HBV or HBsAg positive > 6 months up to now.

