3. With qualified liver biopsy within three months before or after Fibrotouch examination for pathological staging.
4. Without chemical therapy history of powerful medicine to lower enzyme in the two weeks before blood biochemistry tests (e.g. dimethyl diphenyl bicarboxylate and bicyclol).
5. Participant agreed and signed the informed consent form.

(II) Exclusion Criteria

1. The people who are unable or unwilling to sign informed consent form.

2. The people who have merger of hepatitis c, alcohol and non-alcoholic fatty liver disease, autoimmune liver disease, inherited metabolic liver disease, biliary systemic disease or liver and gall parasitic diseases.
3. The people who have other serious chronic disorders or history of malignancy.
4. The people with ALT ≥ 5 ULN in the past 1 month.
5. The people with $WBC < 3.5 \times 10^9/L$, $PLT < 60 \times 10^9/L$, $PTA < 60\%$.
6. The people with $DBIL \geq 1.5$ ULN.
7. The people with decompensated cirrhosis (especially the people with ascites).
8. Pregnant or lactating women, or women who has a pregnant plan and don't want to birth control in the study period.
9. The people who have wound on the right upper abdomen recently.
10. The people who have various space-occupying tumor or cyst in right liver.
11. The people who have none or limited legal capacity.

(III) Study method

1. Outpatients and inpatients with chronic hepatitis B and compensatory liver cirrhosis, conforming to the inclusion criteria and signing the ICF.
2. Collection of materials and specimen:
 - ◆ Collection of clinical materials: Fill in the uniformly-printed CRF and keep or duplicate the original medical record.
 - (1) Name, sex, age, illness course, family history of infectious diseases and hereditary diseases, drinking history, pharmacotherapy history, and history of chronic diseases (e.g. essential hypertension, heart disease and diabetes).
 - (2) Physical examination: Height (cm), weight (kg), body mass index ($BMI = \text{weight}/\text{height}^2$), heart rate (bpm), respiratory rate (times/min), blood pressure (mmHg).
 - ◆ Retaining of hematological specimen: Within one week before the FibroTouch examination, the venous blood is drawn at an empty stomach, and the different portions of

blood are kept: 2ml whole blood (freeze in two 2ml tubes); 8ml completely-separated serum (freeze in four 2ml tubes); and 3ml plasma (freeze in two 2ml tubes). Keep the tube at -80°C, and uniformly send it to the central laboratory.

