◆ Retaining of liver puncture specimen: Fix with 10% neutral formalin, retain additionally 6 white films at every unit, and send it to the pathological examination center (the quality control is shown in Appendix 1).

3. Hematological examination: (the quality control is shown in Appendix 1)

(1) Routine blood tests;

(2) PT, PTA, INR;

(3) TP, ALB, AST, ALT, CHE, GGT, ALP, TBA, TBIL, DBIL, GLU, TC, TG, HDL, LDL, BUN, Cr;

(4) AFP;

(5) Serum virological indices: hepatitis B test (five-item), HBV-DNA assay, HCV antibody test, HIV antibody test; HDV antigen test.

4. Ultrasonic examination:

Within three months after the liver biopsy, the ultrasonic examination is made at an empty stomach for ≥ 8 h. The inner diameter of liver, spleen, gallbladder, portal vein and splenoportal vein is measured through the ordinary two-dimensional ultrasonic examination. The echo data of liver surface/edge/parenchyma and gallbladder wall is scored to evaluate the severity of fibrosis. At every center, the operation should be made via the fixed machine by the fixed person, so as to prevent the artificial error; and the ultrasonic examination, the elasticity determination of liver tissues and the collection of medical history should be made in the same day.

Semi-quantitative Scoring Criteria at Liver Ultrasonic Examination

Score Item	1 score	2 scores	3 scores
Liver surface (Ls)	Smooth, flat	Unsmooth, fine water ripple	Wave, saw-shaped or discontinuous
Liver parenchyma (Lp)	Fine spot, uniform distribution	Slightly enhanced, coarse particle of non-uniform	Obviously echo enhanced, particulate or nodular echo group

		distribution	
Gallbladder wall (G)	Smooth	Coarse, slightly thickened	Obviously thickened or two-side sign

5. Liver Stiffness Measurement (LSM)

Within 3 months before and after the liver biopsy, the liver stiffness measurement (LSM) values are determined via FibroTouch.

◆ Investigators will operate the FibroTouch system to measure the patients' values of liver stiffness and fat attenuation parameters according to the SOP of FibroTouch.

<1>. Subjects lie in face-up position, and stretch his or her right arm to the maximum extent or cross behind his or her head. Enter the name, gender, birth date, medical card No., height, weight and other information into patient information log in FibroTouch system.

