6.2 Operation procedure

(1) Keep in a supine position, lift up both hands to expose the intercostal gap in the area of right liver lobe of chest, and take a deep breath to make the intercostal gap as large as possible at the time of determination.

(2) Vertically stick the probe smeared with coupling agent to the intercostal gap.

(3) Determination site: Select the intercostal gap at the anterior or middle axillary line between the Rib 8~10 for routine determination, or adjust the determination site until the optimal one according to the real-time audiovisual diagram if the determination fails at the routine site.

(4) Observe the audiovisual diagram displayed in the instrument, and press the emission button for determination when there is a laminar liver image.

(5) Determine effectively for 10 times, and regard the mean of these 10 determinations as the determination result.

7. Liver biopsy

Within 3 months before the FibroTouch examination, puncture the 16G liver biopsy needle into 1.5~2.0cm of liver tissues (≥ 8 complete portal areas), fix with 10% neutral formalin, embed with paraffin wax, make the continuous section for HE, Masson and reticular fiber staining (make the HE staining at every study unit, and send another 6 white films to the central laboratory). Then, three pathologists interpret the films independently according to the standard and modified Chevallier semi-quantitative scoring method in the “Protocol for Prevention and Treatment of Viral Hepatitis (2001)”. The interpretation result of these three pathologists should be verified as well consistent through the Kappa test, and otherwise the specimen of inconsistent interpretation result is sent for central interpretation and evaluation.

(1) The liver fibrosis is staged and scored through the following protocol:

① National Protocol for Prevention and Treatment of Viral Hepatitis (2000): staging of liver fibrosis

② Chevallier System (SSS scoring)

③ Metavir System

④ Ishak System

(2) Evaluation protocol for inflammatory activity level and histological activity index (HAI):

① National Protocol for Prevention and Treatment of Viral Hepatitis (2000): grading of inflammation severity

② Ishak Modified HAI: ____/18 (maximum score)

③ METAVIR System: histological activity score

(IV) Safety Evaluation

1. Clinical Safety Evaluation

The clinical safety is evaluated through the adverse events reported by the patients or observed by the doctors.

2. AE

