Definition: Any adverse medical event reported by the patients or observed by the doctors from the signing of ICF and recruitment into study to the final follow-up, either at a causality correlation with the study device or not.

(1) AE record

During the study, the occurrence time of AE, its correlation with study device, its severity, duration, countermeasures and prognosis should be recorded strictly by the facts.

The AEs should be recorded into the assigned CRF of adverse events.

(2) Judgment criteria for AE severity

◆ While filling in the CRF, the investigators will describe the intensity of AE in the following grading criteria:

Mild: No influence on the normal function of subjects;

Moderate: A certain influence on the normal function of subjects;

Serious: Obvious influence on the normal function of subjects.

(3) Judgment criteria for correlation between AE and study device

The investigators should evaluate the possible correlation between AE and study device in the following principles:

- ① Whether there is a rational precedence relation between the starting time of FibroTouch examination and the occurrence time of AE;
- ② Whether the suspicious AE conforms to the known type of AE for this device;
- ③ Whether the suspicious AE can be interpreted by the clinical state of patients or the influence of other therapies;
- ④ Whether the AE disappears or is relieved after the suspension of examination.

According to the above principles, the correlation is classified into 5 grades: definitely relevant, probably relevant, possibly relevant, possibly irrelevant and irrelevant.

(4) SAE:

◆ Judgment of SAE: Under one or more following conditions, the AE is regarded as a SAE: ① Death; ② Life-jeopardizing (e.g. risk of immediate death); ③ Induced or prolonged hospitalization; ④ Influenced working ability; ⑤ Permanent or serious

disability; ⑥ Congenital malformation or defect. If a certain medical event of no death, life-jeopardization or hospitalization may harm the patient or require the medicines or surgery to prevent the occurrence of above conditions in the viewpoint of study doctor, such event should also be regarded as SAE.

◆ Treatment of SAE: If the AE is irrelevant to study device and does not seriously influence the patient and the patient can be followed up as scheduled, the study should be continued. Under the other conditions, the patient should drop out.

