◆ Recording and reporting of SAE: Any SAE during this study should immediately be reported to the supervisor, sponsor and national medicine clinical study institution (i.e. leading unit), which should report to the Ethic Committee and then within 24h to the CFDA and health administrative departure Meanwhile, the investigators must fill in the “Reporting Form of Serious Adverse Events”, and record the occurrence time, severity, duration, countermeasures and prognosis of SAE. If a patient suddenly dies during the study, such event should be reported as SAE, and the autopsy report should be enclosed if any.

(V) Quality Control and Quality Assurance of Clinical Study

◆ The participants must pass the uniform training on the uniform recording method and judgment criteria.

◆ The investigators must work strictly according to this protocol, fill in all study materials in an accurate timely complete neat way, so as to ensure the true reliable contents of report.

◆ Any observation result and finding during this study should be verified so as to ensure the reliability of data and guarantee that every conclusion of clinical study stems from raw data. At the stage of clinical study and data processing, there should be corresponding measures for data management.

◆ During this study, the clinical supervisor will regularly or irregularly make the field supervisory visit to the study center. According to the relevant regulations, the supervisor has the right to check the original record and remind/urge the investigators to carefully normatively complete the study work; and the investigators are liable to coordinate with such work.

(VI) Ethical Requirements and Informed Consent

◆ No subject can be enrolled in the study before he or she express his/her willingness to participate in this study in written statement. To make this decision, subjects should be informed of content of this study and the potential risks and benefits involved.

The investigator must inform this information in both spoken and written form. Informed consent should be obtained from the participants (or legally authorized representative or Witness, if applicable) prior to any other study assessment. A copy of the signed Informed consent form (ICF) will be given to patients.

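### The subject number is issued only after the biopsy stage is entered, so a patient scanned before that point can be registered, or not, with both results known

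*Combined protocol and SAP*

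**What the plan says.** Section VII describes one route to a subject number, through the central web system: "After the investigator logs in the system and fills in the pathological stages, this system will" assign it from what has been entered. No number at consent is described.

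The order of scan and biopsy is stated in four places, and they do not agree:

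- Section IX (I), criterion 3, allows either order: "With qualified liver biopsy within three months before or after Fibrotouch examination for pathological staging".
- Section IX (III), item 5, also allows either order: "Within 3 months before and after the liver biopsy, the liver stiffness measurement (LSM) values are determined via FibroTouch".
- Section IX (III), item 4, puts the ultrasound after the biopsy and requires the elasticity measurement on the same day as the ultrasound: "Within three months after the liver biopsy, the ultrasonic examination is made at an empty stomach". That implies biopsy first.
- Section IX (III), item 7, puts the biopsy first: "Within 3 months before the FibroTouch examination, puncture the 16G liver biopsy needle".

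Consent is to be obtained "prior to any other study assessment" (section IX (VI)), and data may be collected once it is signed. Adverse events count "from the signing of ICF and recruitment into study to the final follow-up" (section IX (IV), 2).

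The recruitment target in section V is expressed in qualified cases: "≥ 600 qualified cases are included to guarantee 500 final statistical cases", with at least 100 in each of five stage groups. The analysis population is divided only after the database is frozen (section IX (VIII), 8.7).

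**The concern.** This point is about who enters the dataset, not about blinding of readers or operators. A diagnostic accuracy estimate is protected when patients are entered before either result is known. Here the reference result is the trigger for entry, and for some patients the index result may already be in hand. The site could then leave out a patient whose scan failed, who never had a usable biopsy, or whose two results disagreed.

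The text gives no consecutive-enrolment rule, no log of consented patients and no rule for recording failed scan attempts. An unreliable FibroTouch result is simply repeated until it is reliable (section IX (III), item 5). The stage minimums in section V give a site a further reason to choose whom it registers.

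At stake are the primary accuracy estimates and the FibroTouch versus FibroScan success-rate comparison, which is tested against a 10-point non-inferiority margin. Both could be computed on a set selected on the index test, the reference result or both, with no count of those left out.

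**Working it through.** **1. Who can be scanned before having a number**

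- *Scan-first patient* (criterion 3 and item 5): consent, scan, biopsy within three months, stage reading, stage entry, number. The stiffness value is known throughout. At registration both results can be known.
- *Biopsy-first patient* (items 4 and 7): the site can enter the stage and obtain the number before the scan, but nothing requires it to. The scan may follow the biopsy by up to three months. Staging involves three independent readers, with central re-reading if they disagree. A scan before stage entry is therefore possible on this order too.

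The affected group is every patient scanned before stage entry. The documents do not state its share, which could be anywhere from none to all.

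**2. The plan's own figure**

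Inputs from section V: expected sensitivity 0.61, lowest acceptable 0.55, alpha 0.05, power 80%. Sidedness is not stated. A one-sided exact binomial test first reaches 80% power at n = 423 (power 0.803, actual alpha 0.0495, rejection at 250 or more positives), which matches the plan. Then 423 / 0.80 = 528.75, rounded up to 529, which also matches. The design therefore rests on a gap of 0.61 − 0.55 = 0.06.

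**3. How much selective non-registration would fill that gap**

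Assumptions, not document values: true sensitivity s = 0.55; a share d of false negatives is not registered; all true positives are registered.

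Observed sensitivity = s / [s + (1 − s)(1 − d)]

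| d | Calculation | Observed sensitivity |
|---|---|---|
| 0.10 | 0.55 / (0.55 + 0.405) | 0.576 |
| 0.22 | 0.55 / (0.55 + 0.351) | 0.610 |
| 0.30 | 0.55 / (0.55 + 0.315) | 0.636 |

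The d that gives exactly 0.61 is 1 − (0.55 × 0.39 / 0.61) / 0.45 = 0.219. That is 0.45 × 0.219 = 0.098, or about 10% of stage-positive patients.

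With 423 registered stage-positive patients and the test in step 2, the chance of rejecting 0.55 when it is the true value is 0.05 with no loss, 0.13 at d = 0.05, 0.28 at d = 0.10 and 0.73 at d = 0.20.

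**4. Two limits on that illustration**

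- *Share affected.* If only a share w of stage-positive patients is scanned before stage entry, and sensitivity is the same in both groups, replace d by w × d. With d = 0.22 and w = 0.5, the result is 0.55 / (0.55 + 0.45 × 0.89) = 0.579. With w = 0 there is no effect.
- *Direction.* If 10% of true positives were lost instead, the result is 0.495 / (0.495 + 0.45) = 0.524. Equal proportional loss from both groups leaves 0.55 unchanged.

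**5. Adverse events**

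Events are to be recorded from consent, and serious events reported immediately, with no condition that a number exists. What the text does not say is how an event that occurs before numbering is tied to a numbered case report form, or what happens to it if the patient is never numbered. The phrase about recruitment in the definition also leaves the exact start of the window unclear.

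**The case against.** The strongest reply is that the trial may in practice run biopsy first. Items 4 and 7 of section IX (III) both imply it, and it fits section VII: the stage is entered, the number issued and the scan then done, so a failed scan falls on a numbered subject. The sample size also allows for 80% effective determinations, which makes most sense if ineffective scans occur among included cases. This stands as a limit on the size of the problem. It does not remove it, because criterion 3 and item 5 permit the other order and no text puts stage entry before the scan.

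Several stronger readings are tempting and are not supported:

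- *That unregistered patients leave no record.* The device's patient log, the saved and printed result, the U-disk copy and the medical record are all called for at the site. What is missing is a numbered central record and a place in a denominator.
- *That adverse-event counts from consent must be incomplete.* The duty to record and report does not depend on a number. The gap is one of linkage.
- *That an 80% success rate could be reported as 100%.* The 80% in section V is determination effectiveness. The secondary endpoint is successful detection, and the background section treats the two as different measures (effective 99% vs 72%; successful 100% vs 97%). Both devices are also used on the same day, so an unregistered patient is lost to both sides of the comparison, and the effect on the difference cannot be derived from the documents.
- *That sensitivity will be inflated.* The FibroTouch cut-off is chosen from the completed ROC data, so no study cut-off exists at registration to label a patient a false negative. A site could only guess, for instance from the FibroScan cut-offs in the background section.

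Finally, a patient without a qualified biopsy fails criterion 3 and is outside the accuracy analysis by design. Numbering at consent would count such patients; it would not supply their reference result or remove verification bias.

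**Conclusion.** The concern holds as a design weakness. The stated registration rule, together with the permitted test order, allows inclusion to depend on the index result, the reference result or both, and the trial database could not show how many patients were lost. This is a rule that permits selection, not merely a missing detail. The documents give no evidence that selection occurred.

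Its size is not known. Because the planned gap is only 0.06, losing about 22% of false negatives (about 10% of stage-positive patients) would by itself move a true 0.55 to the planned 0.61. That figure assumes that only false negatives are lost and that all stage-positive patients are scanned before stage entry. Other patterns of loss would give a smaller shift, none, or a shift downwards. The adverse-event part is minor and limited to linkage.

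**What to change.** - Amend section VII so that the web system issues the subject number when consent is signed, before the FibroTouch scan. This works under either test order.
- Make stage entry a later, time-stamped step in the same system and run the stage counts from it. State what happens to a numbered patient whose stage group is already filled.
- Reconcile criterion 3 and items 4, 5 and 7 of section IX (III) on the order of scan and biopsy.
- For the FibroTouch versus FibroScan success rate, use all patients with an attempted scan as the denominator. All numbered patients would be too wide, since some will withdraw or prove ineligible before any scan.
- Link adverse events from consent onwards to the number issued at consent.
- Report numbered patients without a qualified biopsy or without a valid stiffness value, by reason and by test order.

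The cost is a reconfiguration of the registration system and a short amendment. Some numbers will go to patients who never become evaluable, so the patient flow will look less complete. No procedure is added for patients.

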◆ A successful and effective test by FibroTouch must meet the following requirements: ultrasonic-A signal does not have intensive and rapid shaking, and does not fluctuate significantly in different depth; ultrasonic-M signal does not have big difference of lightness and displays a laminar distribution pattern in different depth; ultrasonic-E signal presents a routine white-and-black twill diagram.

◆ Each subject will obtain 10 successful acquisitions and the median value of these acquisitions will be considered as the examination result of LSM and FAP. The IQR-to-median ratio of the 10 acquisitions should be ≤ 0.3 (the smaller the IQR value, the reliable the result is). If the result is not reliable, it should be detected again until the result is reliable.

◆ To avoid artificial errors, the instrument needs to be operated by a fixed professional in each site, and all information will be documented in a uniform model and stored in U-disk, keep by a designated personnel.

6. FibroScan Examination

6.1 At the same site as that for FibroTouch, the stiffness of liver is determined via Fibroscan at the same day.

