◆ By grouping according to the grading result via golden standard, the inter-group comparison is made on the FibroTouch determination results through the variance analysis or Wilcoxon rank-sum test, the correlation between two groups is tested through the Spearman correlation analysis, and the correlation coefficient (r) and 95% CI are calculated for two groups.

◆ By regarding the different grading results of golden standard as the judgment critical point, the curve of receiver operating characteristic (ROC) for elasticity value is constructed. The subjects are grouped by regarding the different determination results of elasticity value as the judgment critical point, the sensitivity/specificity is calculated according to the grading result of golden standard, the ROC curve is plotted through the X-axis of specificity, the Y-axis of sensitivity and the calculated result, and the area under curve and its 95% confidence interval are calculated. The critical value corresponding to whichever is greater for the result of sensitivity and specificity is regarded as the judgment critical point for FibroTouch determination value, and then the corresponding sensitivity, specificity, positive predicted value and negative predicted value are calculated.

Comparison of secondary objective: by statistically assuming the success rate of FibroTouch is non-inferior to that of Fibroscan, the critical value of non-inferiority is 10%; and by statistically assuming the determination result of FibroTouch is equivalent to that of Fibroscan, the critical value of equivalence is 1.5KPa.

In the above analysis, $P < 0.05$ indicates a significant difference.

(VIII) Data Management and Data Traceability

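### The success-rate non-inferiority test does not define success, and the two devices are measured under different reliability and repeat rules

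*Combined protocol and SAP*

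**What the plan says.** The first secondary objective (section II (II)) is "Difference between FibroTouch and FibroScan in the rate of d successful detection". Under Statistical Analysis of Data (section IX (VII)), the hypothesis is that "the success rate of FibroTouch is non-inferior to that of Fibroscan, the critical value of non-inferiority is 10" per cent. No section defines success at patient level, gives its denominator, or says whether the first or the final attempt is scored.

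The measurement rules are in section IX (III).

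- **FibroTouch (item 5).** "A successful and effective test by FibroTouch must meet the following requirements"; those requirements concern the quality of the A, M and E signals. Ten successful acquisitions are then taken at one position. "The IQR-to-median ratio of the 10 acquisitions should be" at most 0.3, and "If the result is not reliable, it should be detected again until the result is reliable". No maximum is given.
- **FibroScan (item 6.2).** "Determine effectively for 10 times, and regard the mean of these 10 determinations as the determination result". There is no IQR limit and no order to repeat an unreliable set. The operator may use another site: "or adjust the determination site until the optimal one according to the real-time audiovisual diagram if the determination fails at the routine site". No cap is given here either.

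The background section reports two separate rates from a study of 214 patients, FibroTouch against FibroScan: effective detection 99% against 72%, and successful detection 100% against 97%.

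**The concern.** A non-inferiority comparison of success rates means something only if both devices can fail in the same way. Here only FibroTouch has a reliability limit to miss, and only FibroTouch must repeat a completed set until that limit is met. A site that follows the protocol therefore has little opportunity to record a final unreliable FibroTouch result. If final reliability is what is scored, the measurement rule rather than the device may decide the test.

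At stake is a secondary claim with its own hypothesis and margin. If sites do not note which set was the first and how it ended, the first-set outcome cannot be recovered at analysis.

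**Working it through.** **The plan's own figures.** The plan gives no sample size or power for the success-rate test. Its only related figure is the 80% determination effectiveness in section V. The 423 cases for sensitivity (0.61 against 0.55) reproduce with a one-sided exact binomial test at 0.05 (power 0.803), and 423 / 0.80 = 528.75, rounded up to 529. So the planners allowed for 20% non-evaluable examinations.

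**Inputs.** From the plan: margin 10% (taken as 10 percentage points) and 500 final cases. Assumed, because the plan does not give them: one-sided 0.025 (the plan states only P < 0.05), first-set success pC = 0.80 for FibroScan and pT = 0.65 for FibroTouch (15 points worse, beyond the margin), and independent device results (the two examinations are paired, but their correlation is not given).

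**Formulas.**
- Success after r sets with independent failures: 1 − (1 − p)^r.
- Chance of passing: Φ((pT − pC + 0.10)/SE − 1.96), with SE = √[pT(1 − pT)/500 + pC(1 − pC)/500].

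**Reading 1: success is a final reliable result.**
- First sets only: SE = √(0.000455 + 0.000320) = 0.0278; Φ(−0.05/0.0278 − 1.96) = Φ(−3.76), about 0.01%.
- One FibroTouch repeat: 1 − 0.35² = 0.878; SE = 0.0231; Φ(0.1775/0.0231 − 1.96) = Φ(5.7), about 100%.
- Two FibroTouch repeats: 1 − 0.35³ = 0.957; about 100%.

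The one-repeat result is also about 100% for other pairs 15 points apart: 97% against 82% (82% becomes 96.8%) and 72% against 57% (57% becomes 81.5%).

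**Persistent failures.** Let a share q of first-set failures never succeed. With one repeat, and the remaining failures succeeding at 65%, the rate is 0.65 + 0.35(1 − q)(0.65). With unlimited repeats it tends to 1 − 0.35q.

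| q | One repeat | Chance of passing | Unlimited repeats | Chance of passing |
|---|---|---|---|---|
| 0.25 | 82.1% | 99.8% | 91.3% | about 100% |
| 0.50 | 76.4% | 69% | 82.5% | 99.9% |
| 0.75 | 70.7% | 4.4% | 73.8% | 29% |
| 1.00 | 65.0% | 0.01% | 65.0% | 0.01% |

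The one-repeat figures depend on the model. If the patients who can succeed share one constant per-set rate, q = 0.50 gives 78.8% (93% chance of passing) and q = 0.75 gives 72.7% (17%). The limit under unlimited repeats is the same.

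**Reading 2: success is 10 valid acquisitions, whatever the IQR.** The repeat order is triggered by unreliability, not by failure to acquire. It does not change the rate, and the test keeps its nominal error of 2.5% at the margin.

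**Reading 3: first sets are scored, with the IQR limit applied to FibroTouch only.** Suppose both devices acquire 10 valid readings in a share s of patients, and a share r of those sets are reliable. FibroTouch scores s × r and FibroScan scores s. Two identical devices then differ by s(1 − r), against FibroTouch.

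**How much the definition can matter.** In the background study the FibroScan rate is 97% on one definition and 72% on the other. That is 25 points, or 2.5 times the margin.

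**The case against.** The strongest reply is that nothing in the plan says the test counts repeats. FibroTouch success is described by signal quality, reliability is checked afterwards, the background section separates successful from effective detection, and the objective speaks of successful detection. On that reading (Reading 2) the repeat rule does no harm. This stands as a plausible reading, but the plan does not adopt it.

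A reader might infer that retries are allowed for one device only. The documents do not support that: FibroScan's change of site is also a retry, also uncapped, and triggered by failure itself. What is one-sided is the reliability limit and the order to repeat until it is met.

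A reader might also infer that the bias always favours FibroTouch. Reading 3 shows that it can run the other way.

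The 65% is purely illustrative. The only comparative rates in the documents favour FibroTouch on both measures. The inflation also depends on failures being curable by repetition, and it vanishes if all persist.

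Finally, the 80% effectiveness allowance fits poorly with repeating until reliable, but it does not contradict it outright. It may simply show that the planners expected some examinations to remain non-evaluable despite the instruction.

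**Conclusion.** The concern holds in this form: the test compares the devices on an undefined success rate, under validity and repeat rules that differ between them. This is more than missing detail, because the rules that are stated already make the comparison unlike for unlike.

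The direction and size of any bias depend on the missing definition. Under final-result scoring, a device 15 points worse on the first set could go from about a 0.01% chance of passing to about 100% with one independent repeat. With three quarters of failures persistent, the chance is 4.4% to 17% with one repeat, depending on the model, and 29% with unlimited repeats. These figures rest on the assumed first-set rates, 500 patients, one-sided 0.025 and independent device results. They show what the rule permits; they do not predict that an inferior device will pass.

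The point should be fixed. It touches a secondary objective only; the primary accuracy analysis and its sample size are unaffected.

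**What to change.** In section IX (VII), define success for both devices by one common validity criterion, applied to the first set of 10 acquisitions. State whether that criterion includes an IQR-to-median limit and, if so, apply it to both devices. State the denominator. Record each set and its outcome for both devices, including FibroScan attempts at a changed site. Repeat sets may still supply the LSM value for the accuracy analysis, and the final-result rate may be reported descriptively.

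Allowing both devices the same maximum number of sets would not be enough. In the 65% against 80% example with independent failures, one repeat each gives 87.8% against 96.0% and a 17% chance of passing. Two repeats each give 95.7% against 99.2% and about 100%. Equal retries shrink the difference towards zero against a fixed margin.

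The cost is a short protocol definition and one recorded field (set number and outcome), with no extra procedure. The case report form is not among the documents, so it may already hold this field. The FibroTouch success rate may come out less favourable. The change has to be in place before patients are measured.
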